5.8 Outcomes Research Assessments

No additional QLQ collection is required with Revised Protocol 12.

5.9 Other Assessments

5.9.1 Immunogenicity Assessments

Serum samples for analysis of development of ADA will be drawn in conjunction with analysis of lirilumab, nivolumab, and ipilimumab serum concentrations and will be collected from all as indicated in [Section 5.7.3.3](#). These serum samples will be analyzed for ADA by a validated immunoassay. [REDACTED]

[REDACTED] Samples designated for PK analysis ([Section 5.5](#)) may be used for immunogenicity analysis in the event of insufficient volume, to complete the immunogenicity assessment, or to follow up on suspected immunogenicity-related AEs. Effective with Revised Protocol 12, PK and ADA samples will continue to be collected but will not be analyzed except as clinically indicated in specific cases such as Grade 3/4 toxicity, infusion reactions, etc.

6 ADVERSE EVENTS

An *Adverse Event (AE)* is defined as any new untoward medical occurrence or worsening of a pre-existing medical condition in a clinical investigation subject administered an investigational (medicinal) product and that does not necessarily have a causal relationship with this treatment. An AE can therefore be any unfavorable and unintended sign (such as an abnormal laboratory finding), symptom, or disease temporally associated with the use of investigational product, whether or not considered related to the investigational product.

The causal relationship to study drug is determined by a physician and should be used to assess all AEs. The causal relationship can be one of the following:

Related: There is a reasonable causal relationship between study drug administration and the AE.

Not related: There is not a reasonable causal relationship between study drug administration and the AE.

The term “reasonable causal relationship” means there is evidence to suggest a causal relationship.

AEs can be spontaneously reported or elicited during open-ended questioning, examination, or evaluation of a subject. (In order to prevent reporting bias, subjects should not be questioned regarding the specific occurrence of one or more AEs.)

Immune-mediated AEs are AEs consistent with an immune-mediated mechanism or immune-mediated component for which non-inflammatory etiologies (eg, infection or tumor progression) have been ruled out. IMAEs can include events with an alternate etiology, which were exacerbated by the induction of autoimmunity. Information supporting the assessment will be collected on the subject’s CRF.

6.1 Serious Adverse Events

A *Serious Adverse Event (SAE)* is any untoward medical occurrence that at any dose:

- results in death
- is life-threatening (defined as an event in which the subject was at risk of death at the time of the event; it does not refer to an event which hypothetically might have caused death if it were more severe)
- requires inpatient hospitalization or causes prolongation of existing hospitalization (see **NOTE** below)
- results in persistent or significant disability/incapacity
- is a congenital anomaly/birth defect
- is an important medical event (defined as a medical event(s) that may not be immediately life-threatening or result in death or hospitalization but, based upon appropriate medical and scientific judgment, may jeopardize the subject or may require intervention [eg, medical, surgical] to prevent 1 of the other serious outcomes listed in the definition above). Examples of such events include, but are not limited to, intensive treatment in an emergency room or at home for allergic bronchospasm; blood dyscrasias or convulsions that do not result in

hospitalization). Potential drug-induced liver injury (DILI) is also considered an important medical event. (See Section 6.6 for the definition of potential DILI).

Suspected transmission of an infectious agent (eg, pathogenic or non-pathogenic) via the study drug is an SAE.

Although pregnancy, overdose, cancer, and potential DILI are not always serious by regulatory definition, these events must be handled as SAEs. (See Section 6.1.1 for reporting pregnancies).

Any component of a study endpoint that is considered related to study therapy (eg, death is an endpoint, if death occurred due to anaphylaxis, anaphylaxis must be reported) should be reported as SAE (see Section 6.1.1 for reporting details).

NOTE:

The following hospitalizations are not considered SAEs in BMS clinical studies:

- a visit to the emergency room or other hospital department < 24 hours, that does not result in admission (unless considered an important medical or life-threatening event)
- elective surgery, planned prior to signing consent
- admissions as per protocol for a planned medical/surgical procedure
- routine health assessment requiring admission for baseline/trending of health status (eg, routine colonoscopy)
- medical/surgical admission other than remedying ill health state and planned prior to entry into the study. Appropriate documentation is required in these cases
- admission encountered for another life circumstance that carries no bearing on health status and requires no medical/surgical intervention (eg, lack of housing, economic inadequacy, care-giver respite, family circumstances, administrative).
- admission for administration of anti-cancer therapy in the absence of any other SAEs

6.1.1 Serious Adverse Event Collection and Reporting

Following the subject's written consent to participate in the study, all SAEs, whether related or not related to study drug, must be collected, including those thought to be associated with protocol-specified procedures. All SAEs must be collected that occur during the screening period and within 150 days of discontinuation of dosing. If applicable, SAEs must be collected that relate to any later protocol-specified procedure (eg, a follow-up skin biopsy).

The investigator should report any SAE occurring after these time periods that is believed to be related to study drug or protocol-specified procedure.

An SAE report should be completed for any event where doubt exists regarding its status of seriousness.

If the investigator believes that an SAE is not related to study drug, but is potentially related to the conditions of the study (such as withdrawal of previous therapy, or a complication of a study procedure), the relationship should be specified in the narrative section of the SAE Report Form.

SAEs, whether related or not related to study drug, and pregnancies must be reported to BMS (or designee) within 24 hours. SAEs must be recorded on the SAE Report Form; pregnancies on a

Pregnancy Surveillance Form (electronic or paper forms). When using paper forms, the reports are to be transmitted via email or confirmed facsimile (fax) transmission to:

SAE Email Address: See Contact Information list.

SAE Facsimile Number: See Contact Information list.

For studies capturing SAEs/pregnancies through electronic data capture (EDC), electronic submission is the required method for reporting. The paper forms should be used and submitted immediately, only in the event the electronic system is unavailable for transmission. When paper forms are used, the original paper forms are to remain on site.

SAE Telephone Contact (required for SAE and pregnancy reporting): See Contact Information list.

If only limited information is initially available, follow-up reports are required. (Note: Follow-up SAE reports should include the same investigator term(s) initially reported.)

If an ongoing SAE changes in its intensity or relationship to study drug or if new information becomes available, a follow-up SAE report should be sent within 24 hours to BMS (or designee) using the same procedure used for transmitting the initial SAE report.

All SAEs should be followed to resolution or stabilization.

6.2 Non-serious Adverse Events

A *Non-serious Adverse Event* is an AE not classified as serious.

6.2.1 Non-serious Adverse Event Collection and Reporting

The collection of non-serious AE information should begin at initiation of study drug. Non-serious AE information should also be collected from the start of a placebo lead-in period or other observational period intended to establish a baseline status for the subjects.

Non-serious AEs should be followed to resolution or stabilization, or reported as SAEs if they become serious (see [Section 6.1.1](#)). Follow-up is also required for non-serious AEs that cause interruption or discontinuation of study drug and for those that are present at the end of study treatment as appropriate. All identified non-serious AEs must be recorded and described on the non-serious AE page of the CRF (paper or electronic).

Completion of supplemental CRFs may be requested for AEs and/or laboratory abnormalities that are reported/identified during the course of the study.

Every AE must be assessed by the investigator with regard to whether it is considered immune mediated. For events that are potentially immune mediated, additional information will be collected on the subject's CRF.

6.3 Laboratory Test Result Abnormalities

The following laboratory test result abnormalities should be captured on the non-serious AE CRF page or SAE Report Form (paper or electronic) as appropriate:

- Any laboratory test result that is clinically significant or meets the definition of an SAE

- Any laboratory test result abnormality that required the subject to have study drug discontinued or interrupted
- Any laboratory test result abnormality that required the subject to receive specific corrective therapy.

It is expected that wherever possible, the clinical, rather than laboratory term would be used by the reporting investigator (eg, anemia vs low hemoglobin value).

6.4 Pregnancy

If, following initiation of the investigational product, it is discovered that a study subject is pregnant or may have been pregnant at the time of investigational product exposure, including during at least 6 half-lives after product administration, the investigational product will be permanently discontinued in an appropriate manner (eg, dose tapering if necessary for subject safety).

The investigator must immediately notify BMS (or designee) Medical Monitor of this event and complete and forward a Pregnancy Surveillance Form to BMS (or designee) within 24 hours and in accordance with SAE reporting procedures described in [Section 6.1.1](#).

Follow-up information regarding the course of the pregnancy, including perinatal and neonatal outcome and, where applicable, offspring information must be reported on the Pregnancy Surveillance Form.

Any pregnancy that occurs in a female partner of a male study subject should be reported to BMS. Information on this pregnancy will be collected on the Pregnancy Surveillance Form.

6.5 Overdose

An overdose is defined as the accidental or intentional administration of any dose of a product that is considered both excessive and medically important. All occurrences of overdose must be reported as an SAE (see Section 6.1.1 for reporting details).

6.6 Potential Drug-induced Liver Injury

Wherever possible, timely confirmation of initial liver-related laboratory abnormalities should occur prior to the reporting of a potential DILI event. All occurrences of potential DILIs, meeting the defined criteria, must be reported as SAEs (see Section 6.1.1. for reporting details).

Potential DILI is defined as:

1) Aminotransferase (ALT or AST) elevation $> 3 \times \text{ULN}$

AND

2) Total bilirubin $> 2 \times \text{ULN}$, without initial findings of cholestasis (elevated serum alkaline phosphatase),

AND

3) No other immediately apparent possible causes of aminotransaminases elevation and hyperbilirubinemia, including, but not limited to, viral hepatitis, pre-existing chronic or acute liver disease, or the administration of other drug(s) known to be hepatotoxic.

6.6.1 Potential Drug-induced Liver Injury for Subjects with HCC

Potential DILI for this study is defined as:

Hepatotoxicity as evidenced by any of the following:

- AST or ALT $> 10 \times$ ULN for > 2 weeks,
- AST or ALT $> 15 \times$ ULN irrespective of duration,
- Total bilirubin $> 8 \times$ ULN irrespective of duration for subjects with elevated total bilirubin at study entry or $> 5 \times$ ULN for those with normal total bilirubin at entry,

Clinical deterioration manifested by drug-related hepatic decompensation not identified above.

6.7 Other Safety Considerations

Any significant worsening noted during interim or final physical examinations, electrocardiograms (ECGs), x-ray films, any other potential safety assessments required or not required by the protocol should also be recorded as a non-serious or serious AE, as appropriate, and reported accordingly.

6.8 Treatment Algorithms for Drug-related Adverse Events

Treatment algorithms for the management of potential drug-related AEs are located in [Appendix 1](#) of this protocol and in the IB for nivolumab.¹⁹

7 DATA MONITORING COMMITTEE AND OTHER EXTERNAL COMMITTEES

For all parts of the study, a blinded independent review committee will review all available tumor assessment scans to determine response using RECIST v1.1 criteria. When required, adjudicated events will be submitted to health authorities for review on a specified timeframe in accordance with the adjudication documentation.

8 STATISTICAL CONSIDERATIONS

8.1 Sample Size Determination

8.1.1 Dose Escalation (Part 1; Completed)

As this is a Phase 1/2 dose escalation cohort, the sample size at each dose cannot be determined exactly, as it depends on the number of observed toxicities. Between 3 and 12 subjects approximately are expected to be treated during dose escalation in each Dose Level, and up to 15 subjects may be dosed at selected Dose Levels.

8.1.2 Cohort Expansion (Part 1; Completed)

During cohort expansion, approximately 18 subjects are expected to be enrolled in each of the 3 unknown or low historic response cohort expansions and approximately 35 subjects in the 2 cohorts with higher historic ORR and treated at the previously determined MTD, MAD, or at an alternative dose that is not to exceed the MAD.

CRC, SCCHN, and HCC cohorts: The sample size for each tumor cohort will be guided by a 2-stage Gehan design.³⁸ In order to determine whether a target ORR is likely in a tumor cohort, 9 subjects will be treated at Stage 1 in each tumor type, as outlined in [Table 3.1.1.2-1](#). For a tumor

type in which no responses are observed, it will be concluded that the true ORR is unlikely to be greater than or equal to the target ORR and no more subjects will be enrolled in these tumor cohorts. Otherwise, for the tumor cohort(s) in which at least 1 response among the first 9 subjects is observed, up to an additional 9 subjects will be enrolled as guided by Table 3.1.1.2-2. With 9 subjects in Stage 1, per tumor there is no more than a 10% chance of declaring that there is no therapeutic effect when actually there is an effect. A total of up to 18 subjects across the 2 stages per tumor will guarantee an estimate of the true ORR with 12% precision.

NSCLC and MEL cohorts: A total of approximately 35 subjects will be enrolled in each of these tumor cohorts based on achieving a higher precision with a reasonable control on the type I error. In a cohort of approximately 35 subjects, if 12, 14, or 16 responses are observed, then the lower limit of the 1-sided 90% CI for the ORR is 24%, 29%, or 34%, respectively. In addition, 19 responses would need to be observed in approximately 35 subjects so that the 90% 1-sided CI for the ORR is entirely above 20%. These calculations are based on the lower limit of the Clopper-Pearson method for exact CIs. If the true ORR in a tumor type is 45%, then with approximately 35 subjects in a cohort there is 96% chance of observing at least 10 responses, and 93% chance of observing at least 11 responses, and there is 7% chance of observing 10 or fewer responses (false negative rate). If the true ORR for a tumor is only 30% rather than 45%, then there is a 35% and 14% chance, respectively, that there will be at least 12 or at least 14 responses in approximately 35 subjects (false positive rate).

The above numbers are approximate, as subjects treated during dose escalation with a tumor under the same setting (eg, dose and population) as in cohort expansion may be included in the total n per tumor.

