In each of the NSCLC and MEL cohorts, approximately 35 subjects will be enrolled to allow for a more precise estimate of the ORR in these tumors following combination treatment. The sample size for the other 3 cohorts will be guided by Gehan³⁸ design. In order to determine if a target response rate (eg, 25 to 30%) is likely, an initial number of subjects (eg, 9) will be treated at first (Stage I) in a cohort, as outlined in Table 3.1.1.2-1. In the tumor cohort in which no responses are observed, it will be concluded that the true response rate is unlikely to be greater than or equal to the target rate and no more subjects will be enrolled in that cohort. Otherwise, in the cohorts in which at least 1 response among the Stage I subjects is observed, up to 9 additional subjects will be treated for a total of 18 subjects per tumor type, as guided by Table 3.1.1.2-2. In Stage I, approximately 9 subjects will be enrolled per tumor type. The number of subjects enrolled in Stage II per tumor cohort will be guided by the number of responders observed in Stage I and the required precision of the ORR estimate. This is summarized in Table 3.1.1.2-2 below, using a precision of 12% around the ORR point estimate.

Table 3.1.1.2-1: Tumor Types Eligible for Cohort Expansion

Tumor Type	Stage I Subjects	Stage II Subjects	Total Subjects
NSCLC	N/A	N/A	Approx. 35
MEL	N/A	N/A	Approx. 35
CRC	9	4 to 9	Approx. 9 to 18
SCCHN	9	4 to 9	Approx. 9 to 18
HCC	9	4 to 9	Approx. 9 to 19
Totals			Approx. 97 to 124

Approx. = approximately; N/A = not applicable.

The actual sample size per cohort in Stage II to achieve desired precision (standard error) of 12% for the ORR estimate, as guided by the Gehan design, depends on the number of responses observed in Stage I (see Table 3.1.1.2-2), assuming a target ORR of 25% to 30%.

Table 3.1.1.2-2: Cohort Expansion Sample Sizes by n of Responses in Stage I for CRC, SCCHN, and HCC Tumors

Stage I Number of Responses in the First 9 Subjects	Stage II n ^a	Total n/Cohort
0	0	9
1	4	13
2	8	17
3	9	18

Table 3.1.1.2-2: Cohort Expansion Sample Sizes by n of Responses in Stage I for CRC, SCCHN, and HCC Tumors

Stage I Number of Responses in the First 9 Subjects	Stage II n ^a	Total n/Cohort
4	8	17
5	5	14
6	0	9

^a Based on 12% precision for the ORR estimates and a target ORR of 25% to 30%.

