5.2 Cohort Expansion (Part 1; Completed)

During cohort expansion, approximately 18 subjects are expected to be enrolled in each of the 3 unknown or low historic response cohort expansions and 35 subjects in the 2 cohorts with higher historic ORR and treated at the previously determined MTD, MAD, or at an alternative dose that is not to exceed the MAD.

CRC, SCCHN, and HCC cohorts: The sample size for each tumor cohort will be guided by a 2-stage Gehan design.²¹ In order to determine whether a target ORR is likely in a tumor cohort, 9 subjects will be treated at Stage 1 in each tumor type, as outlined in Table 2.1.1.2-1. For a tumor type in which no responses are observed, it will be concluded that the true ORR is unlikely to be greater than or equal to the target ORR and no more subjects will be enrolled in these tumor cohorts. Otherwise, for the tumor cohort(s) in which at least 1 response among the first 9 subjects is observed, up to an additional 9 subjects will be enrolled as guided by Table 2.1.1.2-2. With 9 subjects in Stage 1, per tumor there is no more than a 10% chance of declaring that there is no therapeutic effect when actually there is an effect. A total of up to 18 subjects across the 2 stages per tumor will guarantee an estimate of the true ORR with 12% precision.

NSCLC and MEL cohorts: Thirty-five subjects will be enrolled in each of these tumor cohorts based on achieving a higher precision with a reasonable control on the type I error. In a cohort of 35 subjects, if 12, 14, or 16 responses are observed, then the lower limit of the 1-sided 90% CI for the ORR is 24%, 29%, or 34%, respectively. In addition, 19 responses would need to be observed in 35 subjects so that the 90% 1-sided CI for the ORR is entirely above 20%. These calculations are based on the lower limit of the Clopper-Pearson method for exact CIs. If the true ORR in a tumor type is 45%, then with 35 subjects in a cohort there is 96% chance of observing at least 10 responses, and 93% chance of observing at least 11 responses, and there is 7% chance of observing 10 or fewer responses (false negative rate). If the true ORR for a tumor is only 30% rather than 45%, then there is a 35% and 14% chance, respectively, that there will be at least 12 or at least 14 responses in 35 subjects (false positive rate).

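### The Gehan cohorts are said to be guaranteed a 12% standard error, but the plan's own Stage II table allows up to 13.5% after 1 Stage I response, up to 13.4% after 5, and 15.7% after 6

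*Protocol*

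**What the plan says.** Protocol 8.1.2 sets the design for the CRC, SCCHN and HCC cohorts: "The sample size for each tumor cohort will be guided by a 2-stage Gehan design". It then gives the precision claim: "A total of up to 18 subjects across the 2 stages per tumor will guarantee an estimate of the true ORR with 12% precision". The synopsis (Statistical Methods, Sample Size Determination) makes the same claim with an approximate 18, and SAP 5.2 repeats that the two stages "will guarantee an estimate of the true ORR with 12% precision". None of the three sentences is conditional on the Stage I result or on the true ORR.

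Protocol 3.1.1.2 says what precision means. Stage II sizes are chosen "to achieve desired precision (standard error) of 12% for the ORR estimate", with a target ORR of 25% to 30% assumed. On the first stage it says: "In Stage I, approximately 9 subjects will be enrolled per tumor type". Table 3.1.1.2-2 then fixes the total by the number of Stage I responses. Synopsis Table 3 and SAP Table 2.1.1.2-2 carry the same figures.

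**The concern.** A cap of 18 subjects does not mean that 18 are enrolled. The table shrinks Stage II when Stage I shows few responses or many, and after 6 of 9 it enrolls nobody further. The SE of a proportion depends on n and on the final response rate, so a cohort that stops at 9, 13 or 14 subjects need not reach an SE of 12%.

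At stake is the accuracy of a stated design property. A reader of Protocol 8.1.2 or SAP 5.2 would take every cohort that shows at least one response to have an ORR known to within an SE of 12%. The plan does not secure that, and most of the shortfall falls on the rows with 5 or 6 Stage I responses.

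**Working it through.** **Inputs.** Stage I n = 9 and SE target 0.12 (Protocol 3.1.1.2). Stage II n = 4, 8, 9, 8, 5, 0 for 1 to 6 Stage I responses, so total n = 13, 17, 18, 17, 14, 9 (Table 3.1.1.2-2). Target ORR 25% to 30%.

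**Step 1: reproduce the table.** Gehan's second-stage rule sets total n = ceil[pU(1 − pU)/0.12²], where pU is an upper limit for the Stage I rate. Take pU = x/9 + z·sqrt[(x/9)(1 − x/9)/9] with z = 1.150, the normal-approximation limit of a two-sided 75% interval. The documents do not state this limit; it is inferred because it fits.

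| Stage I responses x | pU | pU(1 − pU)/0.0144 | Stage II n | Table |
|---|---|---|---|---|
| 1 | 0.2316 | 12.36 | 4 | 4 |
| 2 | 0.3816 | 16.39 | 8 | 8 |
| 3 | 0.5141 | 17.35 | 9 | 9 |
| 4 | 0.6350 | 16.10 | 8 | 8 |
| 5 | 0.7461 | 13.16 | 5 | 5 |
| 6 | 0.8474 | 8.98 | 0 | 0 |

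Every row matches. Each size is therefore one at which the SE is at most 12% if the true rate equals pU. It carries no such promise at rates nearer 50%.

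**Step 2: final SE under each row.** SE = sqrt[p(1 − p)/n], with p = total responses / total n, over every total that the row allows.

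| Stage I responses | n | Possible totals | SE range |
|---|---|---|---|
| 1 | 13 | 1 to 5 | 7.4% to 13.5% (4/13 = 12.8%, 5/13 = 13.5%) |
| 2 | 17 | 2 to 10 | 7.8% to 12.1% |
| 3 | 18 | 3 to 12 | 8.8% to 11.8% |
| 4 | 17 | 4 to 12 | 10.3% to 12.1% |
| 5 | 14 | 5 to 10 | 12.1% to 13.4% (maximum at 7/14) |
| 6 | 9 | 6 | 15.7% |

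Examples: sqrt[(5/13)(8/13)/13] = 0.135; sqrt[0.5 × 0.5/14] = 0.134; sqrt[(6/9)(3/9)/9] = 0.157. After 1 response, 12% is exceeded only if 3 or 4 of the 4 Stage II subjects respond.

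**Step 3: what a guarantee would need.** p(1 − p) is largest at 0.25, so n ≥ 0.25/0.0144 = 17.4, that is 18. At n = 18 the maximum SE is sqrt(0.25/18) = 11.8%.

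**Step 4: SE with the true ORR fixed at the target.**

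| n | ORR 25% | ORR 30% |
|---|---|---|
| 9 | 14.4% | 15.3% |
| 13 | 12.0% | 12.7% |
| 14 | 11.6% | 12.2% |
| 17 | 10.5% | 11.1% |
| 18 | 10.2% | 10.8% |

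**Step 5: how often the final SE exceeds 12%.** Sum the binomial probabilities of all Stage I and Stage II results with SE > 0.12, over the tabulated rows 0 to 6.

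| True ORR | 1 resp. | 2 | 4 | 5 | 6 | Total | Total with SE ≥ 12.5% |
|---|---|---|---|---|---|---|---|
| 25% | 1.1% | 0.1% | 1.3% | 3.9% | 0.9% | 7.3% | 5.9% |
| 30% | 1.3% | 0.3% | 3.1% | 7.4% | 2.1% | 14.2% | 10.7% |

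The last column drops the 12.1% results (8/17, 9/17 and 10/14), which round to the stated 12%. Seven to nine Stage I responses have no row in the table and are left out; their total probability is 0.1% at 25% and 0.4% at 30%.

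**The case against.** The strongest defence is that 12% is described as a desired figure, under a Gehan plan, at a target ORR of 25% to 30%. On that reading n=13 and n=14 meet it at 25% (12.0% and 11.6%), and only the 6-response row misses badly, at a probability of about 1% to 2%. This lowers the weight of the point but does not save the sentence. At 30% the SE is 12.7% at n=13, 12.2% at n=14 and 15.3% at n=9, and the guarantee carries no such condition. Protocol 8.1.2 also calls its numbers approximate, but the reason it gives is that matching dose-escalation subjects may be counted in n; that does not qualify the guarantee.

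A reader might go on to infer three stronger things that the documents do not support.

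- *The table is miscalculated, or the cohorts are too small.* It is not a calculation error: a standard Gehan rule reproduces every row.
- *Reported ORRs will carry a false precision.* SAP 7.5 reports ORR with a two-sided 95% Clopper-Pearson interval, and no 12% SE enters any output. SAP 7.1 combines Parts 1 and 2 and summarizes efficacy by tumor type, and Part 2 adds about 35 SCCHN subjects, so the reported SCCHN ORR does not rest on 9 to 18.
- *The guarantee fails a third to a half of the time.* The same enumeration gives 35% at a true ORR of 40% and 46% at 45%, but these rates lie outside the stated target and the counts include the 12.1% results.

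**Conclusion.** The guarantee is wrong as written. It holds strictly only for a cohort that reaches 18 subjects, and to rounding at 17. It can fail at 13, and it fails for every outcome at 14 and in the 6-response row at 9. The excess is at most about 1.5 points after 1 to 5 Stage I responses and 3.7 points after 6. Within the plan's target ORR the chance of exceeding 12% is about 7% to 14%, or 6% to 11% if only an SE of 12.5% or more is counted.

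This rests on the documents' definition of precision as a standard error, on the usual binomial SE at the observed rate, and on the table being followed exactly with 9 subjects in Stage I. The 75% limit in Step 1 is an inference; the SE results do not depend on it.

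Severity is low. Part 1 has completed enrollment, and no sample size, stopping rule or planned analysis changes. The shortfall does fall mainly on high-response cohorts, but a reader should not infer that it bears on which cohorts are taken forward: Revised Protocol 12 closed Parts 3 and 5 and removed Parts 4 and 6 after later SCCHN data showed no differential efficacy signal.

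**What to change.** In Protocol 8.1.2, the synopsis and SAP 5.2, replace the guarantee sentence with: *Stage II sizes target a standard error of about 12%; the final standard error may range from about 7% to 13.5% when 1 to 5 responses are seen in Stage I, and is about 16% when 6 are seen; at most 12% is assured only at n=18.*

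The tables stay as they are. The cost is a text edit in three places, and the stated precision becomes slightly less favourable. No subjects are added.
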